2.4. Randomization

Eligible participants are enrolled on InForm, which allocates each participant a random predefined order during which to take the study interventions. The Imperial Clinical Trials Unit (ICTU) generates these random codes and supplies them to the production pharmacy.

3. Study schedule

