6.1. Primary outcome (Hypothesis 2)

Hypothesis 2: Overall >50% of symptom burden is nocebo rather than pharmacological.

For the trial, all participants receive a smartphone or, if they prefer, the application can be downloaded to their existing phone. Access to the phone will allow them to record real-time daily documentation of symptoms experienced on a visual analogue scale of 0-100.

Participants will rate symptoms every day, with the daily scores averaged into a monthly score.

SAMSON STATISTICAL ANALYSIS PLAN

January 14, 2020

Page 6

Each participant receives four months (4×28 days) each of no medication, placebo, and active medication (i.e, statin). We represent the individual participant's symptom score data as follows:

$$\begin{array}{ccc} x_{0_1} & x_{p_1} & x_{s_1} \\ x_{0_2} & x_{p_2} & x_{s_2} \\ x_{0_3} & x_{p_3} & x_{s_3} \\ x_{0_4} & x_{p_4} & x_{s_4} \end{array}$$

$$\bar{x}_0 = \frac{\sum_{j=1}^4 x_{0_j}}{4} = \frac{\sum_{j=1}^4 ((\sum_{i=1}^{28} x_{0_{ij}})/28)}{4}, \bar{x}_p = \frac{\sum_{j=1}^4 x_{p_j}}{4} = \frac{\sum_{j=1}^4 ((\sum_{i=1}^{28} x_{p_{ij}})/28)}{4}, \bar{x}_s = \frac{\sum_{j=1}^4 x_{s_j}}{4} = \frac{\sum_{j=1}^4 ((\sum_{i=1}^{28} x_{s_{ij}})/28)}{4}$$

\bar{x} - mean symptom score for no medication, placebo, statin, i -day 1 to 28 of treatment month, j - treatment month 1 to 4

We assume no carry-over effect. Thus, the estimated mean of the effect of nocebo is calculated as follows:

$$\text{Mean nocebo effect} = \sum_{n=1}^N \left(\frac{\bar{x}_{p_n} - \bar{x}_{0_n}}{\bar{x}_{s_n} - \bar{x}_{0_n}} \right) / N$$

N = number of study participants

Because the study participants are independent of each other, the variance of the estimated mean can be calculated as the sum of variances of the individual participants:

$$\text{Variance of the mean nocebo effect} = s^2 = \sum_{n=1}^N s_n^2 = \sum_{n=1}^N \text{Var} \left(\frac{\bar{x}_{p_n} - \bar{x}_{0_n}}{\bar{x}_{s_n} - \bar{x}_{0_n}} \right)$$

To calculate the variance of the estimate, we use a Taylor series approximation, which is a function of the variance of the numerator, variance of the denominator, and the covariance of the two:

$$1) \text{Var}(\text{numerator}) = \text{Var}(\bar{x}_p - \bar{x}_0) = s_p^2 + s_0^2 - 2r_{s_p, s_0} s_p s_0$$

$$2) \text{Var}(\text{denominator}) = \text{Var}(\bar{x}_s - \bar{x}_0) = s_s^2 + s_0^2 - 2r_{s_s, s_0} s_s s_0$$

CONFIDENTIAL

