$$3) \text{ Cov}(numerator, denominator) = \text{cov}(\bar{x}_p - \bar{x}_0, \bar{x}_s - \bar{x}_0) = \text{cov}(\bar{x}_p, \bar{x}_s) - \text{cov}(\bar{x}_p, \bar{x}_0) - \text{cov}(\bar{x}_0, \bar{x}_s) + \text{cov}(\bar{x}_0, \bar{x}_0) = \text{cov}(\bar{x}_p, \bar{x}_s) - \text{cov}(\bar{x}_p, \bar{x}_0) - \text{cov}(\bar{x}_0, \bar{x}_s) + s_0^2$$

$$\text{where, for example, } \text{cov}(\bar{x}_p, \bar{x}_s) = \frac{\sum_{j=1}^4 (x_{p_j} - \bar{x}_p)(x_{s_j} - \bar{x}_s)}{4 - 1}$$

$$4) s_n^2 = \text{Var}\left(\frac{\bar{x}_p - \bar{x}_0}{\bar{x}_s - \bar{x}_0}\right) = \left(\frac{\bar{x}_p - \bar{x}_0}{\bar{x}_s - \bar{x}_0}\right)^2 \left(\frac{\text{Var}(\bar{x}_p - \bar{x}_0)}{(\bar{x}_p - \bar{x}_0)^2} + \frac{\text{Var}(\bar{x}_s - \bar{x}_0)}{(\bar{x}_s - \bar{x}_0)^2} - 2 \frac{\text{cov}(\bar{x}_p - \bar{x}_0, \bar{x}_s - \bar{x}_0)}{(\bar{x}_p - \bar{x}_0)(\bar{x}_s - \bar{x}_0)}\right)$$

s = standard deviation, s² = variance, r = correlation

The Taylor's series approximation is based on asymptotic theory. Should the data not allow stable estimates of the components of the variance, we will use a bootstrapped estimate of the variance.

To calculate the 95% CI for the mean nocebo effect, the test statistic is $t = \sqrt{N}(\mu - \mu_0)/\sqrt{s^2}$

The null hypothesis is rejected if $t > t_{\alpha, N-1}$ where, in SAS, $t_{\alpha, N-1}$ is TINV(1- α , N-1);

In SAS, the p value associated with the test statistic T is PVAL=1-probt(abs(T), N-1) or PVAL=cdf('T', T, N-1).

The 95% confidence interval is $\text{Mean nocebo effect} \pm t_{\alpha/2, N-1} \sqrt{s^2} / \sqrt{N}$

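### SAP 6.1 puts the variance of each participant's nocebo ratio on the scale of a single month and pairs months that the random order does not match

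*SAP*

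**What the plan says.** SAP 6.1 defines each participant's score in a condition as the mean of four monthly scores. The index is described only as "j - treatment month 1 to 4", and SAP 2.4 says the system "allocates each participant a random predefined order during which to take the study interventions". Neither document describes blocks or triplets of months.

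For the Taylor-series variance of a participant's ratio, SAP 6.1 gives three components:

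- The variance of the numerator, placebo mean minus no-medication mean, is "s_p^2 + s_0^2 - 2r_{s_p, s_0} s_p s_0". The denominator has the same form: "Var}(\bar{x}_s - \bar{x}_0) = s_s^2 + s_0^2 - 2r_{s_s, s_0} s_s s_0".
- The covariance of numerator and denominator is built from covariances between conditions and ends in s_0², which stands for the covariance of the no-medication mean with itself.
- The example given for a covariance between conditions multiplies j-th deviations and divides by three: "x_{p_j} - \bar{x}_p)(x_{s_j} - \bar{x}_s)}{4 - 1".

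The symbols are glossed only as standard deviation, variance and correlation. A fallback follows: "Should the data not allow stable estimates of the components of the variance, we will use a bootstrapped estimate of the variance". SAP 6.1.1 keeps months with at least 10 daily scores and keeps participants with at least one such month per treatment.

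**The concern.** Two things are wrong in the formulas that feed the primary confidence interval and p-value.

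**Scale.** A sum of cross-products over 4 − 1 estimates the covariance of single months. The covariance of two four-month means needs a further division by four.

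**Pairing.** The j-th placebo month and the j-th statin month are different calendar months in a random sequence. Renumbering months within a condition leaves every mean and the ratio unchanged, but it changes every correlation and covariance, and so the standard error.

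Two gaps add to this. The fixed 4 and 4 − 1 have no meaning when months are missing. The fallback has no stated trigger criterion and no resampling unit. What is at stake is an interval that is on the wrong scale and depends partly on how months are labelled.

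**Working it through.** **The plan's own figures.** The SAP states no standard error to reproduce. The only number given for Hypothesis 2 is N = 36 in SAP 4.1. Its printed inputs give (1.96 × 0.29/0.10)² = 32.3, so 33. That calculation uses a between-participant SD and none of the formulas at issue, so the mismatch is a separate matter.

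**Step 1: scale.** Let s² be the sample variance of four monthly scores (divisor 3). The variance of their mean is s²/4. Applying the SAP's covariance formula to the no-medication months paired with themselves returns the sum of squared deviations over 3. The s_0² in the covariance is therefore the one-month variance. The Taylor formula is linear in these terms, so dividing each by 4 divides the participant's variance by exactly 4 and the standard error by exactly 2, whatever the data.

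**Step 2: constructed participant.** The documents give no data, so these scores are assumed:

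| Condition | Months | Mean | s² |
|---|---|---|---|
| No medication | 5, 8, 6, 9 | 7.0 | 10/3 = 3.33 |
| Placebo | 14, 11, 17, 12 | 13.5 | 21/3 = 7.00 |
| Statin | 20, 15, 17, 22 | 18.5 | 29/3 = 9.67 |

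Numerator 6.5, denominator 11.5, ratio R = 6.5/11.5 = 0.565. The formula is Var(R) = [Var(num) + R² Var(den) − 2R Cov]/11.5², with 11.5² = 132.25 and R² = 0.3195.

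- *Unpaired, divided by 4:* Var(num) = (7.00 + 3.33)/4 = 2.583; Var(den) = (9.67 + 3.33)/4 = 3.25; Cov = 3.33/4 = 0.833. Var(R) = (2.583 + 1.038 − 0.942)/132.25 = 0.0203, SE 0.14.
- *SAP formula, months as listed:* Var(num) = 17.00, Var(den) = 11.67, Cov = 5.67. Var(R) = (17.00 + 3.73 − 6.41)/132.25 = 0.108, SE 0.33.
- *SAP formula, placebo renumbered 11, 12, 14, 17 and statin 17, 15, 20, 22:* Var(num) = 3.67, Var(den) = 9.67, Cov = 5.67. Var(R) = (3.667 + 3.088 − 6.406)/132.25 = 0.0026, SE 0.05.
- *SAP formula, placebo 17, 12, 14, 11 and statin 15, 20, 17, 22:* Var(num) = 19.67, Var(den) = 1.67, Cov = −5.67. Var(R) = (19.667 + 0.532 + 6.406)/132.25 = 0.201, SE 0.45.

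The last two are the extremes over all 24 × 24 = 576 pairings. The SAP variance averaged over the pairings is exactly 4.0 times the unpaired value. In 51 of the 576 (9%) the SAP standard error is below 0.14. Dividing by four without removing the pairing still leaves a range of 0.026 to 0.224.

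**Step 3: average inflation.** Simulation of 100,000 participants with 12 randomly ordered months, j taken as chronological, assumed month SD 4 and means 8, 14 and 16. The second column compares the SAP's root-mean-square standard error of the numerator with its true SD. The third compares the SAP's standard error of the ratio with the unpaired s²/4 value, person by person.

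| Month errors | SAP SE / true SD, numerator | SAP SE / unpaired SE, ratio: median (10th to 90th percentile) |
|---|---|---|
| Independent | 1.99 | 1.97 (1.12 to 2.62) |
| AR(1), correlation 0.5 | 1.84 | 1.83 (0.97 to 2.57) |
| Shared linear trend with half the variance | 1.50 | 1.43 (0.73 to 2.21) |

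The unpaired s²/4 form gave 1.00 for the numerator in all three settings.

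**Step 4: effect on the primary interval.** The SAP sums participants' variances, so the missing 1/4 passes through in full and, other things as printed, doubles the half-width. Pairing noise partly averages out. With independent months, SD 4, means 8/14/16 or 8/14/22 and N of 50 or 60, random renumbering typically gave the summed standard error a coefficient of variation of about 4 to 12%. The ratio of its 97.5th to its 2.5th percentile was about 1.2 to 1.6.

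**The case against.** **The symbols may mean something else.** The SAP does not spell out s_p² and s_s². If s² is the variance of a mean, the numerator and denominator identities are correct. The printed covariance would still lack the 1/4, so the terms would be on different scales. In the third calculation of Step 2, this reading gives Var(num) = 3.67/4 = 0.917 and Var(den) = 9.67/4 = 2.417. Cov is (5.67 − 3.33) + 3.33/4 = 3.17. The bracket is then 0.917 + 0.772 − 3.580 = −1.89, a negative variance. So this reading does not rescue the formulas.

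**j may be chronological.** That is a natural reading, and it would fix one numbering and make the interval reproducible. The SAP does not say so, and chronological order gives only a loose link in time between the j-th months of two conditions.

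**Excess width is cautious.** On average the scale error widens the interval and does not favour Hypothesis 2. This stands, but SAP 4.1 aims for ±10%, and for one participant the error can go either way.

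**The protocol has moved on.** Version 1.4, section 8, is later than the SAP and uses one ratio pooled across patients. The SAP's opening section says the SAP governs where the two differ, so the formulas remain in force on paper.

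A reader might also infer three stronger things that the documents do not support. The first is that every individual standard error is twice too large; that holds on average with independent months, not person by person. The second is that the primary interval can move as much as the single example; it sums over participants. The third is a fixed multiple between the Taylor and bootstrap variances. A factor of 5.3 follows only if four months are resampled within a person and the target is a simple mean, and the SAP names no resampling unit.

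**Conclusion.** The concern holds for the governing SAP. The covariance formula, and s_0² with it, is on the single-month scale. On the plain reading the missing 1/4 makes each participant's variance four times too large. The net inflation of the individual standard error averages about 2 with independent months. Under the assumed settings it falls to about 1.8 with autocorrelation and about 1.5 with a strong shared trend and chronological numbering.

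The pairing has no basis in the design. It can move one participant's standard error several-fold in either direction, and it has a smaller but real effect on the primary interval. The formulas are undefined for some participants whom SAP 6.1.1 keeps. The fallback's size relative to the Taylor formula cannot be stated.

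The exact factor of 4 needs no assumption beyond the reading of s². The other sizes rest on the assumed scores, means and month SD. How the SAP combines variances over participants is a separate question, and settling it would not repair this one.

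**What to change.** Choose one method in advance and remove the conditional switch.

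- *If the Taylor formula stays:* replace each s² by s²/m, with m the usable months in that condition. Where m = 1 the within-person s² does not exist, so use a month variance pooled across participants. Set covariances between conditions to zero, so that Cov(numerator, denominator) = s_0²/m_0, or take them from a fitted mixed model.
- *Otherwise:* make a bootstrap that resamples participants the single stated method.
- *If the pooled ratio of protocol version 1.4 is adopted:* delete these formulas from the SAP and bootstrap participants for that ratio.

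The cost is an SAP amendment and a few lines of code. No new data are needed.

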8 STATISTICAL AND DATA ANALYSIS

Our study's principal hypotheses will be tested as follows:

Hypothesis 1 will be tested by calculating the proportion of respondents completing the study, and the corresponding 95% confidence interval for this estimate, and examining whether the confidence interval lies completely above a value of 0.3 or not.

To test **Hypothesis 2**, comparisons between the average monthly symptom burden (measured by the monthly aggregate of symptom scores) resulting from no treatment/placebo/statin treatment periods will be made using a longitudinal multilevel model. The most basic model to test hypothesis 2 would be:

To test **Hypothesis 2**, we will calculate the nocebo ratio across all patients. This is to avoids attempting to analyse the pathological distributions that would arise for patient whose mean statin symptom score is close or less than their no treatment score, because the nocebo ratio becomes disruptively extreme. Combining the data

Confidential Page 14 of 22

SAMSON Protocol No: 1.4

Version 1.4 10th April 2020

across all patients to yield a single statin, placebo and no treatment symptom score allows a representative and interpretable nocebo ratio to be provided.

Hypothesis 3 is that the majority of patients will be taking statins, or have a non-side effect reasons for not doing so, at 6 months after study completion. This will be a descriptive statistic of the sample, which does not require inference of the population mean. No further statistical analysis is therefore necessary

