6.2. Other efficacy outcomes

6.2.1. Hypothesis 1

Hypothesis 1: More than 30% of enrolled participants will complete the study.

- 1) Point estimate $\hat{p} = x/N$ where x is the number of participants who completed the study and N is the number of enrolled participants
- 2) Hypotheses: $H_0: \hat{p} = p_0$ and $H_A = \hat{p} > p_0$ where $p_0 = 0.3$
- 3) Test statistic $z = \frac{\hat{p} - p_0}{\sqrt{p_0(1-p_0)/N}}$
- 4) Reject null hypothesis if $z > z_\alpha$, where $z_{0.05} = 1.645$
- 5) 95% confidence interval: $\hat{p} \pm z_{\alpha/2} \sqrt{\hat{p}(1 - \hat{p})/N} = \hat{p} \pm 1.96 \sqrt{\hat{p}(1 - \hat{p})/N}$

6.2.2. Hypothesis 3

Hypothesis 3: At six months after completion of the study, at least 50% of the participants will either be taking statins or have declined statins for reasons other than perceived side effects.

This hypothesis will be tested in the same way as Hypothesis 1 above but setting $p_0 = 0.5$.

7. Characteristics of the population

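### SAP 6.1 puts s² and the Hypothesis 2 test on different scales and leaves an undefined bootstrap switch open, so the false-positive rate could be about 0%, 5% or 41%

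*SAP*

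**What the plan says.** SAP 6.1 estimates Hypothesis 2 as the mean over N participants of each participant's ratio: placebo minus no tablet, divided by statin minus no tablet. For the variance of that mean it says that "the variance of the estimated mean can be calculated as the sum of variances of the individual participants", and it sets s² equal to the plain sum of the participant variances s_n². Each s_n² comes from a Taylor approximation built on the variances of numerator and denominator and their covariance.

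The fallback follows directly: "Should the data not allow stable estimates of the components of the variance, we will use a bootstrapped estimate of the variance". The SAP does not say what counts as unstable, who decides, whether months or participants are resampled, which variance is targeted, or how many resamples are drawn.

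The closing lines put s² into t = √N(mean − μ0)/√s², tested one-sided on N − 1 degrees of freedom, and into a 95% interval with half-width t × √s²/√N. No value is set for μ0 or alpha in this section.

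Protocol version 1.4, section 8, uses one ratio pooled across patients. It says that individual ratios cause trouble when statin and no-treatment scores are close, "because the nocebo ratio becomes disruptively extreme". The SAP is based on protocol version 1.2 and states that it governs where the two differ.

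**The concern.** Two things need to be fixed before a test is run: which variance is used, and on what scale it enters the formula. SAP 6.1 fixes neither.

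The printed t and interval are right only if s² is the variance of one participant's ratio. The SAP instead calls s² the variance of the mean, and computes something that is neither. A bootstrap that takes the SAP's label at face value is already on the scale of the mean, so the extra √N makes t too large and the interval too narrow. The Taylor sum errs in the other direction.

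The switch may well be used. The Taylor formula divides by differences that can be close to zero. SAP 6.1.1 also admits participants with a single usable month per treatment, for whom no month-to-month variance can be computed. Stability can be judged only on months labelled by treatment, that is, on the primary outcome data. At stake is whether the claim that more than half of the symptom burden is nocebo is declared on the evidence or on the choice of variance.

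**Working it through.** **The plan's own figure.** The only numerical design figure for Hypothesis 2 is the sample size in SAP 4.1. The printed formula gives (1.96 × 0.29/0.10)² = 32.3, so 33, against a stated 36. A t quantile gives 35, and z = 2 with SD 0.30 gives exactly 36. The gap is small and does not affect this point. The SAP states no error rate for either variance route.

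**Inputs.** N = 60 randomised, 50 planned, and SD of individual ratios 0.29 (SAP 4.1). Assumed: μ0 = 0.5, from the wording of Hypothesis 2, and alpha 0.05 one-sided, by analogy with the Hypothesis 1 rule in SAP 6.2.1. The critical value at 59 degrees of freedom is 1.671.

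**Scale.** The variance of a mean of N independent ratios, given their s_n², is Σs_n²/N². The SAP omits the 1/N². Since Σs_n² = N × (root mean square s_n)², its t reduces to (mean − 0.5)/(root mean square s_n). The standard error in use is therefore √N times the one implied by the s_n.

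**The fallback, if it estimates the variance of the mean.** The printed t is then √N times the correct t. At N = 60, √60 = 7.746 and the false-positive rate is P(T > 1.671/7.746) = 41.5%. At N = 50 it is 40.7%. The interval half-width is 0.0097 against a correct value of about 0.075, and coverage is about 20%.

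**Worked example.** N = 60, observed mean 0.60, SD 0.29, s_n = 0.20 for everyone:

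- Printed Taylor: s² = 60 × 0.04 = 2.4; t = 7.746 × 0.10/1.549 = 0.50. Do not reject.
- Bootstrap variance of the mean in the printed t: standard error 0.29/7.746 = 0.0374; t = 7.746 × 0.10/0.0374 = 20.7. Reject.
- Correct scale: t = 0.10/0.0374 = 2.67. Reject.

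Here the first two disagree for observed means from 0.5 + 1.671 × 0.29/60 ≈ 0.508 up to 0.5 + 1.671 × 0.20 ≈ 0.83.

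**Simulated false-positive rates.** Four monthly scores per treatment, independent normal month errors, true mean share 0.5. N = 60, with N = 36 and 50 also run in some settings.

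| Variance put into the printed t | Rate |
|---|---|
| Taylor sum, month SD 2 to 8 | 0.0% |
| Taylor sum, s_n² first divided by 4, month SD 2 or 4 | 0 to 0.9% |
| Taylor sum, month SD 0.5 | 6% |
| Taylor sum, month SD 0.2 | 28% |
| Bootstrap variance of the mean | 39 to 45% |
| Bootstrap replacing each s_n² (months resampled), month SD 3 to 8 | 0% |
| Variance of one participant's ratio | 4.5 to 5.4%; about 3% with near-zero denominators |

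The second row is there because the printed covariance is divided by 3 only. It is therefore a month-level quantity, not one for a four-month mean. The low-noise rows show that the sum leaves out between-participant spread: at month SD 0.2 the root mean square s_n is 0.013 against a true standard error of 0.0369, and 1.671 × 0.013/0.0369 = 0.59, an upper tail of about 28%.

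**Effect of the switch alone.** With both routes put on the scale of the mean, they disagree in about 2 to 8% of null trials (rescaled Taylor rejects in 0 to 14%, participant bootstrap in 5 to 7%). As printed, Taylor and the bootstrap variance of the mean disagree in about 39 to 44% of null trials at ordinary noise.

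**The case against.** The strongest reply is that 41% rests on one reading of one sentence. That sentence follows the formula for a single participant's s_n², and the components it mentions are most directly the variance and covariance terms of that formula. A bootstrap replacing s_n² is at least as faithful to the text, and it gives about 0%, like Taylor. This stands: the documents do not show that 41% is what the analysts would have produced. That the sentence admits three readings with such different error rates is itself the defect.

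The second reply is that the switch is being blamed for a formula error. This also largely stands, since on matched scales the switch alone changes few decisions.

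The third is that protocol version 1.4 has moved to a pooled ratio and treats Hypothesis 2 as a statement about the sample, needing no sample-size calculation. That does not remove the problem, because the SAP claims precedence and still prescribes a population test.

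A reader might infer more: that the two routes always reach opposite decisions, or that the Taylor route makes the claim almost impossible. Neither is supported. The routes agree in most null trials and, in the worked example, outside 0.508 to 0.83. The printed Taylor route rejects in more than 80% of trials at a true share of 0.9 with month SD 3, though in almost none at month SD 5 to 8.

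**Conclusion.** The point holds in this form: as written, SAP 6.1 gives wrong error bars for the primary outcome and does not fix which variance is used. At N = 60 the printed Taylor route is far too conservative at ordinary month-to-month noise (about 0% false positives) and becomes anti-conservative only when that noise is very small. The fallback gives about 41%, 0% or 5% according to reading; the SAP's own label for s² points to the first, but its text does not settle the matter. The missing 1/N² and the repeated √N produce the extremes, and the undefined switch lets the analyst choose between them with the data in hand.

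The figures assume μ0 = 0.5, one-sided alpha 0.05 and independent normal month errors. The 41% depends only on N and the critical value; the Taylor figures depend on the assumed noise. This should be corrected before the primary analysis is relied on.

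**What to change.** Remove the conditional switch and specify one method for the primary outcome whatever the data look like. Resample whole participants with all their months, recompute the Hypothesis 2 estimator each time, and take a percentile interval with a fixed number of resamples and seed (for example 10,000). State that no further √N is applied.

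State μ0 = 0.5 and the alpha. Deciding on the lower limit of a two-sided 95% interval is a one-sided 0.025 test; if one-sided 0.05 is intended, use the lower limit of a 90% interval.

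Name the estimator by reconciling the SAP's mean of participant ratios with the pooled ratio in protocol section 8. This matters because a percentile bootstrap does not cure near-zero denominators if the mean of ratios is kept.

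Report a correctly scaled Taylor interval (Σs_n²/N², no extra √N) only as a sensitivity analysis, with a note that it omits between-participant spread.

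The cost is a few lines of SAP text and a little more programming, with no new data. Keeping the 0.025 level loses some power.

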8.1 POWER CALCULATIONS

Hypothesis 1: We hypothesise that of the patients enrolling for the study, 50% or more will complete the study. Our intention is to report the proportion of patients completing the study and its 95% confidence interval. Based on the binomial principle, $SE_p = \sqrt{p \cdot q/n}$, the number of patients planned after the calculation below (50) will permit this proportion to be stated with a 95% confidence interval of $\pm 1.96\sqrt{\frac{1}{2} \cdot \frac{1}{2}/50}$. Thus the proportion will be reported with a margin of error of $\pm 14\%$

or smaller. If the long-run proportion of patients who would finish the study is ~70%, then a sample size of 50 gives 85% power to detect this at the 5% significance level.

Hypotheses 2 and 3: These hypotheses address the sample of participants and not the population at large. They therefore do not need a sample size calculations.

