This statistical analysis plan (SAP), which is based on protocol Version 1.2 dated August 1, 2019, defines the methods and analyses that Imperial College London plans to use to analyze the data from the Self-Assessment Method for Statin side effects Or Nocebo trial (henceforth, SAMSON). This study adheres to the principles outlined in the Medicines for Human Use (Clinical Trials) Regulations 2004 (SI 2004/1031), amended regulations (SI 2006/1928), and the International Conference on Harmonisation Good Clinical Practice (ICH GCP) guidelines. It is being conducted in compliance with the protocol, the Data Protection Act, and other regulatory requirements as appropriate. If the protocol is subsequently amended, this SAP may be amended as well. Should the SAP and the protocol be inconsistent with respect to the planned analyses, the language of the SAP is governing.

2. Investigational plan

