3.2. Unscheduled visits

Unscheduled assessments are not performed unless participants develop adverse events that the chief investigator considers 'related' to the trial procedure or to atorvastatin therapy.

4. Sample size determination and power calculation**4.1. Sample size calculation – Hypothesis 2**

Each "effect of nocebo" will be a value which, for the sake of the calculation in the protocol, was assumed to be between 0 and 1. The study aims to report an average effect of nocebo for

the population that has a 95% CI of $\pm 10\%$. To achieve this, assuming a conservative scenario of individual-participant values scattered uniformly from 0 to 1 (i.e., $SD = 1/\sqrt{12} = 0.29$), the number of participants to be studied will need to be $\geq N$ where $0.29/\sqrt{N} \leq 0.10/1.96$ (i.e., $N > (1.96 \times 0.29/0.10)^2 = 36$). The investigators planned to recruit 50 participants. In all a total of 62 participants were screened and 60 were randomized.

5. Statistical analysis: general considerations and conventions

Descriptive and inferential statistics will be used to summarize results of the SAMSON study. Continuous variables will be summarized using the number of subjects (N), mean, SD, median, 25th and 75th percentiles, and minimum and maximum. Discrete variables will be summarized using counts and percentages.

Summaries will be provided for demographics, medical history, concomitant medications, and adverse events. For summaries of medical history, concomitant medications, and AEs, the Medical Dictionary for Regulatory Activities (MedDRA®) and the World Health Organization Drug dictionaries, as appropriate, will be used.

All data listings, summaries, and statistical analyses will be generated using SAS® Version 9.4 (or higher) or other validated software.

6. Efficacy analysis

As described in Section 2.3, the study has three hypotheses.

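### SAP 6.1: neither SAS p-value formula for the primary outcome matches the SAP's own upper-tail rejection rule

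*SAP*

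**What the plan says.** SAP 6.1 gives the primary hypothesis a direction: "Overall >50% of symptom burden is nocebo rather than pharmacological". The test statistic is the square root of N times the difference between the estimated mean and mu_0, divided by the square root of s². It is therefore positive when the estimate lies above the null value. The decision rule is upper-tail: "The null hypothesis is rejected if" t exceeds the critical value, which the SAP computes in SAS as `TINV(1-alpha, N-1)`.

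The next sentence gives the p-value: "In SAS, the p value associated with the test statistic T is PVAL=1-probt(abs(T), N-1) or PVAL=cdf('T', T, N-1". Nothing limits either formula to a sign of T, and nothing says which one to use.

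The SAP was written against protocol version 1.2. Its introduction says "Should the SAP and the protocol be inconsistent with respect to the planned analyses, the language of the SAP is governing", and also "If the protocol is subsequently amended, this SAP may be amended as well". Protocol version 1.4, which is later than the SAP, takes a different line on this hypothesis. In section 8 "we will calculate the nocebo ratio across all patients", and section 8.1 says of Hypotheses 2 and 3: "These hypotheses address the sample of participants and not the population at large".

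**The concern.** A p-value should fall below alpha exactly when the stated rule rejects. The rule here looks only at the upper tail, so the p-value must be the upper-tail area beyond T. One printed formula takes the absolute value of T first, and the other takes the lower-tail area. The two are joined by 'or' as if interchangeable, yet for any positive T they are complements of each other.

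At stake is the p-value reported for the primary outcome. A programmer who follows the text could print a value that contradicts the SAP's own decision, in a direction that depends on the formula chosen and on the sign of the result.

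**Working it through.** **Inputs**

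- Direction: the nocebo share is above 50% (SAP 6.1). mu_0 = 0.5 is implied; the section does not write it out.
- Rule: reject if T > `TINV(1-alpha, N-1)` (SAP 6.1).
- Alpha: no number is attached to this test. The 95% interval in 6.1 uses t at alpha/2, and Hypothesis 1 in 6.2.1 uses a one-sided 0.05, so 0.05 is the natural reading. It remains an assumption, and 0.025 and 0.01 were also run.
- N: SAP 4.1 reports "In all a total of 62 participants were screened and 60 were randomized". SAP 6.1.1 allows exclusions, so the analysed N may be lower. N = 50 (planned) and N = 36 (the minimum stated in 4.1) were also run.
- SAS `probt` and `cdf('T', …)` are both taken to return the lower-tail area F(T). This fits the SAP's use of `TINV(1-alpha, …)` as an upper critical value.

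The plan states no numerical p-value, so there is no figure to reproduce. The check is whether each formula agrees with the rule.

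**Formulas, with F the Student t distribution function on N-1 df**

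- p-value matching the rule: 1 - F(T)
- `abs` form: 1 - F(|T|). This equals 1 - F(T) when T ≥ 0, and F(T) when T < 0.
- `cdf` form: F(T), which is 1 minus the matching p-value at every T.

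**Results at N = 60 (59 df)**

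| T | Matching p | `abs` form | `cdf` form | Rule at alpha 0.05 (critical 1.671) |
|---|---|---|---|---|
| +2 | 0.025 | 0.025 | 0.975 | reject |
| +1 | 0.161 | 0.161 | 0.839 | do not reject |
| 0 | 0.500 | 0.500 | 0.500 | do not reject |
| -1 | 0.839 | 0.161 | 0.161 | do not reject |
| -2 | 0.975 | 0.025 | 0.025 | do not reject |

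**Other N, at T = -2** (matching / `abs` / `cdf`)

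- N = 50 (49 df): 0.974 / 0.026 / 0.026
- N = 36 (35 df): 0.973 / 0.027 / 0.027

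**At the rejection boundary.** With alpha 0.05 the critical values are 1.690, 1.677 and 1.671 for N = 36, 50 and 60. At each of them the matching p-value and the `abs` form give 0.05, and the `cdf` form gives 0.95.

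**Agreement with the rule.** At 59 df the critical values for alpha 0.05, 0.025 and 0.01 are 1.671, 2.001 and 2.391. For all three:

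- 1 - F(T) < alpha never disagrees with the rule.
- The `abs` form disagrees for every T below minus the critical value.
- The `cdf` form disagrees for every T beyond the critical value in either direction.

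If the decision were taken from the printed p-value at 0.05, the `abs` form would reject with probability 0.05 + 0.05 = 0.10 at mu_0 under the t reference distribution. The `cdf` form would reject only for T below -1.671, the opposite direction to the hypothesis.

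**The case against.** The strongest reply is that little depends on this line. The rule is stated separately and correctly, and no section says the decision is taken from the p-value. The first formula is right for every T ≥ 0, hence throughout the rejection region, so any result that supports Hypothesis 2 gets the right p-value from it. A value near 0.975 beside an estimate that meets the rule would be noticed. All of this stands, and it limits the error to the reported p-value. It does not make the line correct. No criterion for choosing is given, and choosing by the sign of T does not help, because both formulas print the lower tail when T is negative. If a '1-' was lost before `cdf`, restoring it would repair that form but leave the `abs` form wrong for T < 0. A two-sided reading fails too: neither form is doubled, and the rule is one-sided.

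Second, the line may never be run, because protocol version 1.4 points to a pooled ratio described as a property of the sample. That is a real uncertainty. By the SAP's own precedence clause, however, the line stands until the SAP is amended.

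Third, T has a separate problem. The SAP sets s² to the sum of the participants' variances and divides its square root by √N. The variance of a mean of N independent values is that sum divided by N², so the SAP's standard error is too large by √N. At N = 60, a properly scaled T of 2 becomes 2/√60 = 0.26. As written, T equals (mean - 0.5) divided by the root-mean-square of the participants' s_n. The documents do not give s_n. For assumed values of 0.10, 0.20 and 0.29, |T| > 1.671 needs a mean above 0.67, 0.83 or 0.98, or below 0.33, 0.17 or 0.02. Large |T| may therefore be uncommon unless that scaling is corrected. This affects how often the contradiction would appear. It does not affect the comparison above, which holds T fixed.

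**Conclusion.** The concern holds. Against the SAP's own rule, the `abs` form is wrong for every negative T and the `cdf` form is wrong for every T except zero. At 59 df and T = -2, both print 0.025 where the rule implies 0.975; at T = +2, the `cdf` form prints 0.975 where the rule implies 0.025. The pattern is the same for each N and alpha examined.

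The conclusion rests on the upper-tail rule as written and on the two SAS functions returning lower-tail areas. It does not depend on the unstated alpha, the analysed N or the way s² is computed. The effect is confined to the printed p-value unless someone decides from it. This should be corrected, but it does not undermine the design.

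**What to change.** Replace the sentence in SAP 6.1 with `PVAL = 1 - probt(T, N-1)`, delete both the `abs` and the `cdf` versions, and leave the rejection rule as it is. If the SAP is instead amended to follow protocol version 1.4, with a pooled ratio and no test, remove the p-value line together with the test.

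The cost is one line of SAP text and one line of code. The rule, estimate, confidence interval, data and sample size do not change. The correction makes the p-value agree with the rule for a given T; it does not settle the separate question of how s² is scaled.
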